6.2 RANDOMIZATION AND BLINDING

Eligible participants will be randomised to either intervention or control group in a 1:1 ratio stratified by site. The randomization sequence will be generated by a computer program using random block sizes of 2 or 4 and overseen by the biostatistician at The Hospital for Sick Children. The treatment allocation will be concealed until the point of randomization. Randomization will be done by the local coordinator after informed consent has been obtained. The local coordinator will use REDCap's automatic randomization feature that has been enabled for this project. Due to the nature of the intervention, participants and the local coordinator will be aware of their treatment allocation. Research staff (local and Memotext) will not be blinded to the treatment allocation as they will need to be aware of group assignments for the purposes of onboarding participants to the application and querying any technical questions if participants reach out for assistance.

6.3 STUDY INTERVENTION COMPLIANCE

Compliance to the KiT intervention will be defined as responding to questions posed by the intervention messages and completing questionnaires and PREMs and PROMs at study-specific time-points. If a participant does not reply to the first three intervention messages/questions and/or does not complete the PREMs/PROMs sent by the intervention, two reminders to answer the message and/or PREMs/PROMs will be sent by the intervention, one week apart. If there is still no engagement from the participant, the local coordinator will contact the participant via telephone, SMS or email. The local coordinator will inquire why the participant has not engaged with the intervention and/or why they have not completed the PREMs/PROMs sent to them and ask if they are still interested in participating in this study. Furthermore, as part of the embedded process evaluation, user engagement will be tracked and analyzed to see who is not engaging with the intervention and possible reasons for why. As part of the process evaluation, those who enroll in the study but engage with the intervention only once or not at all or have very sporadic engagement will be invited to participate in a virtual one-on-one interview. These candidates will be contacted by a member of the research team to discuss what could be done to improve their experience. Those who have provided their consent to participate in the process evaluation will be contacted by a member of the research team who will schedule an interview to gather feedback on why they are not engaging with the KiT intervention and what could be improved.

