2 INTRODUCTION

2.1 STUDY RATIONALE

During the transition to adult diabetes care, young adults with type 1 diabetes (T1D) are at risk for deterioration of their diabetes management, having a gap in establishing adult care, and of acute life-threatening complications such as diabetic ketoacidosis. We have shown that there are persistent gaps in transition care services, poor uptake of existing transition resources, and gaps in collaboration and linkages between pediatric and adult diabetes providers. Most digital transition interventions do not offer personalized educational content or resources to support patients based on their stage of transition readiness and they require additional human resources. As a result, existing digital interventions do not adequately engage patients across the transition continuum or demonstrate scalability. *Our study proposes to implement and evaluate a pragmatic digital tool that delivers just-in-time personalized transition education, to improve patient-reported diabetes outcomes and gaps in diabetes care.*

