- 8) The local coordinator will randomize the participant using REDcap's automatic randomization feature. Both the local coordinator and participant will be aware of what study arm they were assigned to as local coordinator will need to explain next steps to the participant depending on study arm and participant will be aware of whether they will receive texts from the KiT intervention.
- 9) Upon randomization, the local coordinator will enter the randomized participant study ID number, randomization arm, mobile phone number, and preferred language in the Research Assistant Participant Enrollment form via Memotext.
- 10) Memotext will send an initial SMS to the participant's mobile phone number, letting them know they are now enrolled in KiT.
 - i. The following SMS will include the first URL link to a REDCap survey that first prompts to participant to complete the baseline KiT survey (demographic information and information about the participant's diabetes care and self-management). When this questionnaire is completed and submitted, the survey will automatically produce the next surveys for participant completion, one at a time: READDY tool questionnaire, SEDM, and BDA Stigma subscale
 1. Some of the content and sequence of the messages and resources sent to the intervention participants will be personalized, based on confidence ratings as measured by the "Readiness of Emerging Adults with Diabetes Diagnosed in Youth" (READDY) tool.
 2. For all participants, if they do not complete the questionnaires within 1 week of receipt, KiT intervention will send a follow-up reminder SMS asking them to complete the questionnaire. This reminder will be sent a maximum of two times (1 week apart). At week three, the local research coordinator will be notified via email by Memotext that the participant has not yet completed their questionnaires and will then follow up with the participant via telephone, SMS or email asking them to complete the questionnaires.
 3. Once the participant completes the questionnaires, they will be sent their \$20 Amazon gift-card via SMS.
 - ii. If the participant is in the intervention arm, after they complete the baseline questionnaires, they will then be sent an SMS with a link to a short enrollment survey where they will learn how to use KiT, access the settings, set up their frequency preferences to receive the content, and set up appointment reminders.

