Intervention arm: both intervention and control groups will continue with their usual diabetes care. In addition, the intervention group will receive the automated text messages for diabetes support and resources tailored according to their level of confidence and interest in transition topics, for 12 months. At baseline, individuals in the intervention group will receive a link via text-message that will take them to a questionnaire about their demographics and diabetes care and self-management, the READDY tool questionnaire, BDA Stigma Subscale, and SEDM on REDCap. Responses to the READDY tool will guide the personalized content of the educational text-messages. During the 12-month intervention period, participants in the intervention group will all receive messages to support participants to navigate diabetes care (e.g. reminders about upcoming appointments, refilling and paying for medication and supplies). At 6 and 12 months after enrollment in this study, all participants (intervention and control arms) will receive links via text messages that link-out to REDCap surveys for completion of: a questionnaire about diabetes care and self-management, SEDM, BDA Stigma subscale, and the READDY tool. Financial compensation will be provided for participant time to complete these outcome measures at baseline, 6, and 12 months.

Control arm: Participants randomized to the control arm will also be offered the same incentives to complete questionnaires (outcome measures) but will not receive any other components of the intervention – no personalized/customized support or diabetes resource messages and no reminders. Control arm participants will continue with their usual T1D transition care. They will be sent prompts via SMS asking them to complete the same questionnaire about diabetes appointments and care, PROMs/PREMs as the intervention group, at the same time-points of baseline, 6 months, and 12 months. The same financial incentive will be offered to both intervention and control groups to encourage participants to respond to these prompts.

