7 DISCONTINUATION AND WITHDRAWAL

7.1 DISCONTINUATION OF STUDY INTERVENTION

Discontinuation from KiT intervention does not mean discontinuation from the study, and remaining study procedures should be completed as indicated by the study protocol.

The data to be collected at the time of study intervention discontinuation will include the following:

- The 6-month or 12-month follow-up questionnaires (dependent on which questionnaire was most recently completed), PROMS (SEDM, READDY, BDA)
- Self or lab- reported A1c at baseline and at 12 months after enrollment to study
- diabetes related ED visits and hospitalizations (measured using health administrative data)
- Aggregate and direct medical costs associated with the intervention and its implementation study data and administrative data)

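### Section 6.3 gives the KiT arm an additional route, through unanswered messages, to a contact that asks about staying in the study, which risks arm-specific loss of the 12-month SEDM

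*Protocol*

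**What the plan says.** Section 6.3 opens the pathway as follows: "If a participant does not reply to the first three intervention messages/questions and/or does not complete the PREMs/PROMs sent by the intervention", then "two reminders to answer the message and/or PREMs/PROMs will be sent by the intervention, one week apart". The next step is conditional: "If there is still no engagement from the participant, the local coordinator will contact the participant via telephone, SMS or email". At that contact the coordinator asks why the person has not engaged with the intervention, or has not completed the "PREMs/PROMs sent to them and ask if they are still interested in participating in this study".

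Three other places bear on this:

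- **Section 6.1.1, control arm.** Controls receive "no personalized/customized support or diabetes resource messages and no reminders". They are still sent the questionnaires at baseline, 6 and 12 months.
- **Section 5.4, step 10.** At baseline, questionnaire follow-up is common to both arms: "For all participants, if they do not complete the questionnaires within 1 week of receipt, KiT intervention will send a follow-up reminder SMS". If the reminders fail, the coordinator asks the person to complete the questionnaires. No question about remaining in the study is described.
- **Section 7.1.** "Discontinuation from KiT intervention does not mean discontinuation from the study". It adds that the remaining study procedures should still be completed.

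**The concern.** Failing to answer content messages is a lapse in using the intervention. Missing a questionnaire is a lapse in outcome follow-up. Section 6.3 treats both alike and, for both, has the coordinator ask about interest in the study as a whole. Since only KiT participants can fail to answer content messages, the least engaged members of one arm can be asked whether they wish to remain in the trial while their questionnaires are up to date. Section 6.2 makes clear that the coordinator knows the allocation.

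A participant who is merely tired of the messages may answer no, although section 7.1 would let that person stop KiT and stay in follow-up. The 12-month SEDM would then be missing. Section 7.2 keeps data already collected unless the participant objects, but it cannot supply a score that was never obtained. Section 8.4 says only that imputation will be considered. If those who leave would have scored lower than those who stay, the loss flatters the KiT arm.

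**Working it through.** **Step 1. Routes to the contact, by arm**

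| Route | KiT arm | Control arm |
|---|---|---|
| No reply to the first three content messages, two weekly reminders, still no engagement | Possible | Not possible (6.1.1: no content messages) |
| Questionnaires not completed, reminders, still no engagement | Possible | Possible |
| Study-level question at the contact (6.3) | Asked on either route | Asked on the questionnaire route |

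The contact itself is common to both arms. The first route is not.

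**Step 2. Timing.** Under section 5.4, steps 10(ii) and 10(iii), KiT content starts after the baseline questionnaires and a short enrolment survey. Someone entering by the non-reply route therefore has a baseline SEDM. If that person leaves at this early stage, the 6- and 12-month scores are missing.

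**Step 3. The plan's own figure.** Section 8.3 claims more than 80% power for a difference of 0.75 with 117 per arm and 20% loss. Evaluable per arm: 117 × 0.8 = 93.6. No SD is given, so the power cannot be reproduced. A two-sided 5% t-test reaches 80% only if the SD is at most about 1.82 (1.816 with 93 per arm, 1.826 with 94). The values 1.6 and 1.82 used below are assumptions; 1.82 is about the largest SD compatible with the claim.

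**Step 4. Illustrative shift.** Let f be the share of KiT participants who would otherwise be followed but leave by this route. Let g be the number of SEDM points by which their 12-month mean would fall below that of the KiT participants who stay. The mean of all is then the stayers' mean minus f × g, so the completer mean is too high by f × g. Neither f nor g is in the protocol.

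| f | g = 0.5 | g = 1.0 | g = 1.5 |
|---|---|---|---|
| 5% | 0.025 | 0.050 | 0.075 |
| 10% | 0.050 | 0.100 | 0.150 |
| 15% | 0.075 | 0.150 | 0.225 |
| 20% | 0.100 | 0.200 | 0.300 |

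Against 0.75 this is 0.025/0.75 = 3% up to 0.300/0.75 = 40%. These are shifts before baseline adjustment.

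**Step 5. Effect on the decision rule.** Section 8.5.2 declares benefit at a posterior probability above 95%. With no true effect, a flat prior (assumed) and 93.6 per arm (held fixed for simplicity), the standard error is SD × √(2/93.6): 0.234 at SD 1.6 and 0.266 at SD 1.82. The chance of declaring any benefit under a shift b is 1 − Φ(1.645 − b/SE):

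| b | SD 1.6 | SD 1.82 |
|---|---|---|
| 0 | 5.0% | 5.0% |
| 0.10 | 11.2% | 10.2% |
| 0.15 | 15.8% | 14.0% |

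**Step 6. Power.** An extra 10 percentage points of loss in the KiT arm alone lowers power from 80.1% to 77.3% at SD 1.82, or from 89.1% to 86.9% at SD 1.6. Any harm would come from selective loss more than from reduced numbers.

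**The case against.** Several stronger readings are tempting, and the protocol does not support them.

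- **That only the KiT arm can trigger the contact.** It cannot be put that way. Uncompleted questionnaires lead to the same contact with the same question, and both arms receive questionnaires. Only the non-reply trigger is exclusive to KiT.
- **That three unanswered messages are enough.** Two reminders a week apart come first, and contact follows only if there is still no engagement.
- **That ordinary readers of information-only messages would be caught.** Section 6.3 defines compliance as responding to questions that the messages pose, and the reminders ask for an answer. Sections 8.1 and 8.5.6 also treat link clicks as engagement, so someone who reads and clicks plausibly never reaches the contact.
- **That the contact invites people to leave.** The text asks about interest and orders no withdrawal. A personal contact may bring some people back, so the net effect on retention has no known sign.
- **That staff contact contaminates the effect of an automated tool.** Section 2.1 faults existing digital tools for lacking content "based on their stage of transition readiness and they require additional human resources". Section 2.2 describes earlier text-message studies as relying on a provider to deliver content, or as simple reminders. A follow-up call to a non-responder is not content delivery.

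The strongest statistical objections concern size. Some people who stay silent through the reminders would be lost whatever is asked, so only the extra loss counts. The primary model adjusts for baseline SEDM, which everyone on the non-reply route has, and so removes the part of the gap that baseline explains. Participants can also pause messages or reduce their frequency (sections 2.3 and 6.1.1), and section 7.3 requires every effort to regain contact.

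All of this limits the concern. It leaves the asymmetric route and the mismatch between sections 6.3 and 7.1, and it does not recover a 12-month score that was never collected.

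**Conclusion.** The point holds in limited form. Section 6.3 gives the KiT arm an additional, engagement-based route to a question about study participation, where section 7.1 would call for a question about the messages alone. This creates an avoidable risk of arm-specific loss of the primary outcome.

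Neither the size nor the net direction can be established from the protocol. The shifts of 0.025 to 0.30 points, and the rise in false declarations of benefit from 5% to 10–16% for shifts of 0.10 to 0.15, rest on assumed leaving rates, score gaps, SDs and a flat prior. They also assume that those who leave would have scored lower, that they would otherwise have been followed, and that baseline adjustment removes none of the gap. They show what such loss could do; they are not an estimate of bias in this trial. The change is worth making because it is cheap and because missing 12-month scores cannot be retrieved at analysis.

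**What to change.** In section 6.3, separate the two triggers.

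1. **Message non-reply.** Ask only about the messages: whether the number works, and whether the person wants them changed, paused or stopped. State that questionnaire follow-up continues whatever the answer. Do not ask about interest in the study.
2. **Missed questionnaires.** Use one identical script in both arms, aimed at completion, as section 5.4 already does at baseline.
3. **Record.** Log each contact by arm and trigger, and report the counts.
4. **Reconcile.** Align section 6.3 with section 7.1. Section 7.2 should be read alongside them, since it lists significant non-compliance with the intervention as a reason for an investigator to withdraw someone from the study.

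The cost is a revised script and a simple log, with no extra staff. Withdrawal on request is unaffected. Section 9 shows that participants are already using KiT, so the first change helps only those who have not yet passed their early messages. The second helps everyone with a questionnaire still to come.

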7 DISCONTINUATION AND WITHDRAWAL

7.1 DISCONTINUATION OF STUDY INTERVENTION

Discontinuation from KiT intervention does not mean discontinuation from the study, and remaining study procedures should be completed as indicated by the study protocol.

The data to be collected at the time of study intervention discontinuation will include the following:

- The 6-month or 12-month follow-up questionnaires (dependent on which questionnaire was most recently completed), PROMS (SEDM, READDY, BDA)
- Self or lab- reported A1c at baseline and at 12 months after enrollment to study
- diabetes related ED visits and hospitalizations (measured using health administrative data)
- Aggregate and direct medical costs associated with the intervention and its implementation study data and administrative data)

7.2 PARTICIPANT DISCONTINUATION/WITHDRAWAL FROM THE STUDY

Participants are free to withdraw from participation in the study at any time upon request.

An Investigator may discontinue or withdraw a participant from the study for the following reasons:

- Withdrawal of informed consent (participant withdrew for any reason)
- Significant study intervention non-compliance
- If the participant meets an exclusion criterion (either newly developed or not previously recognized) that precludes further study participation

Participants who sign the informed consent form, and are randomized and receive the study intervention, and subsequently withdraw, or are withdrawn or discontinued from the study, will be attempted to be replaced if there are at least 12 months remaining in the study so new replacements would receive the full intervention. The data from participants who are withdrawn or discontinued from the study will be used in the analysis unless the participant requests otherwise.

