8.4 POPULATIONS FOR ANALYSES

The conventional frequentist analyses are often interpreted in a dichotomous matter, based on the p-value chosen as threshold for 'statistical significance' and 'no evidence of effect' is confounded with 'evidence of no effect'. A Bayesian analysis will be conducted to provide the probability of any benefit or harm. An intention-to-treat analysis will be conducted by blinded analysts. We will evaluate the extent of missing data to determine if values are missing at random or not and will consider imputation to account for missing values.

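### Section 7.2 lets an investigator withdraw participants from the study for intervention non-compliance, so 12-month SEDM can go missing avoidably and more often in the KiT arm

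*Protocol*

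**What the plan says.** Protocol section 7.2 opens its list with "An Investigator may discontinue or withdraw a participant from the study for the following reasons", and one entry reads "Significant study intervention non-compliance". The withdrawal is from the study, not only from the messages. The decision is discretionary, and the protocol does not say how much non-compliance is significant.

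Section 6.3 defines the term: "Compliance to the KiT intervention will be defined as responding to questions posed by the intervention messages and completing questionnaires and PREMs and PROMs". Section 6.1.1 says that controls get questionnaire prompts but "no personalized/customized support or diabetes resource messages and no reminders".

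Section 7.1 takes a different line for someone who stops the intervention: "Discontinuation from KiT intervention does not mean discontinuation from the study, and remaining study procedures should be completed as indicated by the study protocol".

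On analysis, section 8.4 states "An intention-to-treat analysis will be conducted by blinded analysts", and section 7.2 adds "The data from participants who are withdrawn or discontinued from the study will be used in the analysis unless the participant requests otherwise". The primary comparison in section 8.5.2 is mean SEDM at 12 months. Section 6.2 confirms that participants, local coordinators and Memotext staff all know the allocation.

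**The concern.** Non-engagement with KiT happens after randomisation and can be seen in one arm only. If it can lead to removal from the study, the 12-month outcome goes missing for a reason tied to both arm and engagement, and staff who know the allocation make that decision. If the people removed would have scored lower at 12 months, the observed KiT mean is too high. The estimate then moves from the effect of offering KiT towards the effect in those who used it. The offer is what a pragmatic trial against usual care sets out to evaluate.

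The trial also has other uses for these participants. The process evaluation (section 8.1) seeks out people with little engagement, and the Coincidence Analysis (section 8.5.3) links engagement to outcomes across all participants. Both are weaker without the 12-month outcomes of non-engagers.

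**Working it through.** **1. Whom the clause can reach**

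| Part of compliance (6.3) | KiT arm | Control arm |
|---|---|---|
| Replying to intervention messages | can fail | cannot fail, none are sent |
| Completing questionnaires | can fail | can fail |

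The ground therefore falls unevenly but not exclusively on KiT. Section 6.3 gives no weighting of the two parts.

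**2. Sections 7.1 and 7.2 side by side.** Under 7.1, a participant who stops KiT altogether remains in follow-up. Under 7.2, a participant who is still nominally on KiT but does not reply may be removed from the study. The lesser departure can carry the larger consequence for outcome collection.

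**3. What the data-retention sentence covers.** It keeps what has been collected. A participant withdrawn before month 12 has not yet given the primary outcome, so the sentence cannot supply it. The replacement rule in 7.2 restores numbers, not the outcomes of those removed. It is also worded for people who received the intervention.

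**4. Size, for illustration only.** The protocol gives no SD, no expected withdrawal rate and no outcome gap for non-engagers.

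*Standard error.* Section 8.3 gives 117 per arm, 20% loss, a difference of 0.75 and more than 80% power. Evaluable per arm: 117 × 0.8 = 93.6, taken as 93. The largest SD that gives 80% power with 93 per arm (two-sided 5% t-test, sidedness assumed) is about 1.82. An SD of 1.82 in turn gives 93 per arm, and 93/0.8 rounds up to 117, so the planned size is consistent with an SD of about 1.8.

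- Without gain from baseline adjustment: SE = 1.82 × √(2/93) = 0.267, about 0.27.
- With an assumed baseline correlation of 0.5: SE = 0.267 × √(1 − 0.25) = 0.231, about 0.23.

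*Bias.* Let p be the share of otherwise observed KiT participants who are removed, and D the amount by which their 12-month SEDM falls below that of those retained, after baseline adjustment. Then bias = p × D.

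- p = 10%, D = 0.75: 0.10 × 0.75 = 0.075 points, which is 10% of the 0.75 target.
- p = 15%, D = 1.0: 0.15 × 1.0 = 0.15 points, which is 20% of the target.

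*Chance of declaring any benefit when there is none.* Section 8.5.2 declares benefit above 95% posterior probability. With a flat prior and a normal approximation this chance is P(Z > 1.645 − bias/SE).

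| Bias | SE 0.27 | SE 0.23 |
|---|---|---|
| 0 | 5% | 5% |
| 0.075 | P(Z > 1.367) = 8.6% | P(Z > 1.319) = 9.4% |
| 0.15 | P(Z > 1.089) = 13.8% | P(Z > 0.993) = 16.0% |

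The SE is held at its value before removal. Allowing for the smaller KiT arm lowers these figures slightly: at 15% removed, 79 remain and the range is 13.4% to 15.3%.

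**The case against.** The clause looks like standard template text, and much of the protocol points towards keeping non-engagers. Section 6.3 answers non-response with two reminders, contact by the coordinator and an invitation to interview, and does not mention withdrawal. Section 6.1.1 lets participants reduce or pause messages. Section 7.3 asks for every effort to regain contact. All this makes it less likely that a large share of the arm would be removed. It does not cancel the power that 7.2 grants.

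A reader might infer two stronger charges, and the document supports neither.

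- **That 7.2 breaches intention-to-treat.** Withdrawn participants stay in the analysis set with the data they gave, and section 8.4 says that missingness will be examined and imputation considered. The fault is missing outcome data that the trial need not have created. Imputation does not recover those outcomes, and engagement with messages is recorded in one arm only.
- **That 7.2 flatly contradicts 7.1.** Section 7.1 says that stopping KiT does not in itself end participation, and 7.2 says when an investigator may end it. Both can stand. They collide only when the discretion is used on someone who has merely stopped engaging, which is the case that the wording of 7.2 invites.

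The objection to the figures also stands in part. The share and gap are assumed, the lower SE needs an assumed baseline correlation, and persistent non-engagers may already be among the 20% that section 8.3 expects to lose. If half of those removed would have been lost in any case, p and the bias are halved: the larger scenario falls to 0.075 points and about 9%.

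**Conclusion.** The point holds as a weakness in design and wording. Section 7.2 gives staff who know the allocation an open-ended ground for ending follow-up. One part of that ground can be met only in the KiT arm, and its use would leave the primary outcome uncollected. This works against the evident purpose of 7.1, and it makes an analysis by randomised arm depend on assumptions about outcomes that could have been observed.

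Confidence is high on the text and low on the size. A bias of 0.075 to 0.15 points, with a false declaration of any benefit in roughly 9% to 16% of null trials instead of 5%, rests on these assumptions: 10% to 15% of the arm removed, a baseline-adjusted deficit of 0.75 to 1.0 points, an SE of 0.23 to 0.27, and outcomes that would otherwise all have been obtained. The direction assumes that non-engagers do worse. If they do not, the bias shrinks or reverses, but the avoidable missing data remain. No stated figure in the protocol is shown to be wrong.

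**What to change.** Delete intervention non-compliance from the study-withdrawal list in section 7.2. State there that non-engagement with KiT is recorded as process data and that the 6- and 12-month questionnaires continue to be sought from every randomised participant who has not withdrawn consent, in line with 7.1.

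The cost is one amended line. Questionnaires already go to both arms by SMS. The extra work is some telephone, SMS or email contact by coordinators with non-responders, which sections 5.4 and 6.3 already provide for.
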